#### **Background**

Persistent physical symptoms lead to substantial levels of distress and social costs. Exposure therapy and healthy lifestyle promotion have been found to reduce somatic symptom burden and psychological distress in a large number of conditions where persistent physical symptoms are common, but little is known about the mechanisms responsible for these beneficial effects. Mainstream theoretical models emphasize the role of various forms of symptom preoccupation – the tendency to respond strongly to, and engage in behaviors contingent on, somatic symptoms – in exacerbating somatic symptom burden over time [1-5]. Especially in exposure therapy, but also to some degree in healthy lifestyle promotion, the observed reduction in somatic symptom burden may be likely to be mediated by a reduction in symptom preoccupation. There are also many other processes likely to contribute to the observed treatment effects. Noteworthy examples include increased physical activity [6], the degree to which patients engage with the treatment for example by conducting exposure exercises, and also common factors, i.e., mechanisms common to most psychotherapies, notable examples being the relationship with the therapist [7-10], treatment credibility and the expectancy of future improvement [11, 12].

#### **Aim of this study**

This study aims to evaluate potential mediators, and correlates of key process variables, that could be important for understanding the effects of exposure therapy and healthy lifestyle promotion when delivered to reduce somatic symptom burden and symptom preoccupation in individuals suffering from persistent physical symptoms.

#### **Hypotheses**

Main hypotheses are listed in Table 1.

Table 1. Hypotheses pertaining to tests of mediation.

Note	Outcome	Potential mediator	Hypothesis		
			Exposure	HLP	Between-group
Primary model	Overall somatic symptom burden	Overall symptom preoccupation	Yes, mediation (+)	Yes, mediation (+)	Yes, mediation (a)
Sensitivity analysis 1: general factor	General somatic symptom burden	Overall symptom preoccupation	Yes, mediation (+)	Yes, mediation (+)	Yes, mediation (a)
	Overall somatic symptom burden	Physical activity	Yes, mediation (-)	Yes, mediation (-)	Exploratory
	Overall symptom preoccupation	Physical activity	Yes, mediation (-)	Yes, mediation (-)	Exploratory

In this table “+” stands for a positive relationship, such that a reduction in the mean of the outcome variable is hypothesized to be associated with a reduction in the mean of the potential mediator. Analogously, “-“ stands for a negative relationship, such that a reduction in the mean of the outcome variable is hypothesized to be associated with an increase in the mean of a potential mediator. Exposure, exposure therapy; HLP, healthy lifestyle promotion.

a As prespecified as part of the main study protocol.

### *Other indicators of treatment-specific factors*

We also hypothesize that, in exposure therapy, there will be a Spearman correlation around 0.20-0.40 between the reduction in overall subjective somatic symptom burden (as derived from fitted regression lines) and the average number of reported exposure exercises per week. Moreover, we hypothesize that, in exposure therapy, there will be a Spearman correlation around 0.20-0.40 between the reduction in overall symptom preoccupation (as derived from fitted regression lines) and the average number of reported exposure exercises per week.

### *Other indicators of common factors*

At week 3, participants reported how they perceived the strength of the relationship with the therapist (the working alliance) and to what degree they perceived the treatment as credible and expectancy-evoking. We hypothesize that credibility/expectancy will exhibit Pearson correlations around 0.10-0.50 with previous and subsequent improvement in somatic symptom burden and symptom preoccupation. We hypothesize that working alliance ratings will exhibit Pearson correlations around 0.10-0.40 with previous and subsequent improvement in somatic symptom burden and symptom preoccupation.

## **Methods**

### *Design*

This will be a secondary study of mediators of treatment effects in a randomized controlled trial of exposure therapy versus healthy lifestyle promotion (N=161).

### *Measurement*

All questionnaires are administered online via a simple web interface, with black text on white background and radio buttons to indicate responses. Participants completed a 1-week focus version of the Patient Health Questionnaire 15 (PHQ-15) as a measure of somatic symptom burden on a weekly basis [13], a 1-week focus version of the Somatic Symptom Disorder B-criteria scale 12 (SSD-12) as a measure of symptom preoccupation on a weekly basis [14], and the Godin-Shepard Leisure-Time Exercise Questionnaire (GSLTPAQ) before and after treatment [15]. A study-specific item is administered to measure the number of exposure exercises conducted per week in the exposure treatment. A study-specific item is also administered to measure the development in stressors over the course of the study (Swedish: "Vissa saker kan få vem som helst att må dåligt. Hur stora påfrestningar har du haft i ditt liv under den senaste veckan, t.ex. när det gäller krav från andra, dödsfall, trauma, separation, ekonomi, förlust av arbete eller sjukdom?", rated from "Inte alls påfrestande vecka" to "Extremt påfrestande vecka").

### *Statistical analysis plan*

For this secondary mechanistic study, scoring of the PHQ-15 and SSS-12 will be informed by preceding psychometric evaluation of these scales, focusing on factor structures [16]. From the PHQ-15, items 4 (menstrual problems), 5 (headaches), 8 (fainting spells), and 11 (sexual pain/problems) will not be used for the sum score. The remaining 11 items, unlike the full 15 items, appears to have a stable structure and an important advantage is also that the general somatic symptom burden factor appears to explain just above 50% of the variance in these items, thus supporting simple sum scoring which is not always as straightforward [17]. From the SSD-12, item 7 (reassured by others) will not be used for the sum score. The remaining 11 items, unlike the full 12 items, appears to have a relatively stable, replicated, structure [18].

Prior to the main analyses, key variable distributions and correlations will be evaluated, and change over time visually inspected. Tests of hypotheses pertaining to mediation (Table 1) will then be based on parallel process growth curve models. This main analysis will proceed in three stages: First, models with a random intercept and slope will be built to capture unconditional growth in each of the putative mediators and outcomes. Second, each putative mediator will be entered into the same model as the corresponding outcome, and tests for within-group mediation will concern the slope of the potential mediator (the a-path in the traditional Baron & Kenny mediation framework [19], assuming time to be the independent variable) multiplied by the effect of this slope on the slope of the outcome (equivalent to the b-path in the traditional Baron & Kenny mediation framework, assuming time to be the independent variable). Third, a variable for allocation (exposure therapy vs. healthy lifestyle promotion; 1/0) will be entered and tests for between-group mediation will concern the path from this variable, to the slope of the potential mediator, to the slope of the outcome. All tests of mediation will be bootstrapped (2000 samples) [20].

#### Mediation sensitivity analysis 1: general somatic symptom burden factor

A threat to the interpretation of the primary model is that the PHQ-15, and the 11 items used from this instrument, have a complex factor structure that is not fully reflected by a simple sum. An analogous secondary sensitivity analysis will therefore evaluate the effect on the general somatic symptom burden factor specifically.

Mediation sensitivity analyses 2: stressors experienced over the period (competing process)  
 Another threat to valid conclusions is potential confounding over the a- and b-paths of tests of within-group mediation, and the b-path of tests of between-group mediation. Thus, whenever significant mediating effects are seen, sensitivity analyses will also be conducted to evaluate whether, potentially, the correlation between the mediator and outcome slopes could be explained merely by a corresponding change in stressors over the course of the treatment. In this analysis, assuming that change in stressors can be modelled in a convincing manner, this variable will be entered into the model alongside the mediator and outcome, and paths will be specified from the slope of stressors to both the slope of the mediator and the slope of the outcome before tests for mediation are repeated.

#### Conditional indirect effects

We will test for conditional indirect effects such that the mediated effect (i.e., the influence of a particular change process) depends on the baseline level of the corresponding mediator. For this test, the intercept will be centered at the pre-treatment assessment, and we will test the path from this intercept, to the slope in the mediator (a-path), to the slope in the outcome (b-path) within each treatment.

#### Week-by-week temporal precedence

For outcomes and mediators both measured on a weekly basis, secondary analyses will explore week-by-week temporal precedence of each potential mediator variable relative to the corresponding outcome. This will be modelled using random-intercepts cross-lagged panel models [21], with sensitivity analyses detrended by the inclusion of correlated random slopes which implies that cross-lagged paths are indicative of relationships between deviations from the random intercept and slope, rather than deviations from the random intercept only.

#### Evaluation of exposure exercises, working alliance, and credibility/expectancy

Secondary analyses will also concern the Spearman correlation between the number of conducted exposure exercises and the outcome of exposure therapy in terms of change

derived from fitted slopes. Prior to the analysis of credibility/expectancy, the factor structure for this instrument will be evaluated to determine if it is best conceived of as one score or two separate scores for credibility and expectancy respectively. Pearson correlations will then be calculated to evaluate the relationship between working alliance and credibility/expectancy and change in somatic symptom burden (fitted slopes) and symptom preoccupation (fitted slopes) over time. Within each treatment, working alliance and credibility/expectancy will be tested as a predictor of treatment completion status. In order to assess the relevance of the process variables as contributing to treatment effects, credibility/expectancy and working alliance will also be added to the primary models used to estimate within- and between-group effects on somatic symptom burden and symptom preoccupation for the primary publication.

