After having completed the screening, applicants are contacted for a psychiatric assessment (primarily the MINI) and eligibility interview with a mental health clinician. As is routine practice at the clinic, this may be conducted face-to-face, via telephone, or via a secure video conferencing service. As is routinely done in the primary care clinic, the patient’s general practitioner is consulted whenever further medical evaluation is deemed necessary. Applicants who do not meet eligibility criteria a-k are excluded and referred to routine care, at the clinic if possible, and in accordance with regional healthcare guidelines. Applicants who meet eligibility criteria a-k are encouraged to complete the pre-treatment assessment. Those who do so are randomized (1:1) to flexible internet-delivered exposure-based treatment or the education control and are thereby included as participants in the trial. The subsequent 10 weeks constitute the main phase of the trial during which key measures are administered on a weekly basis (Table 1). At the end of the main phase follows the post-treatment assessment. Follow-up assessments follow 6 and 12 months after therapy.

Table 1. Key outcome measures and assessment points

Questionnaire	Outcome	Reference	SN	PRE	WK	POST	6MFU	12MFU
PHQ-15 (prim.)	Somatic symptoms	(16)	x	x	x	x	x	x
SSD-12	Symptom preoccupation	(20)	x	x	x	x	x	x
SYMPS-prel	Symptom preoccupation	Prel. version	x	x	x	x	x	x
GAD-7	Anxiety	(21)		x		x	x	x
PHQ-9 ^a	Depression	(22)	x	x		x	x	x
WHODAS 2.0	Disability	(23)	x	x		x	x	x
HAI-14	Health anxiety	(29)	x					
AUDIT, DUDIT	Alcohol, drug use	(30, 31)	x					
C/E scale	Credibility/expectancy	(24)			w. 3			
WAI-6	Relationship w. therapist	(25)			w. 3			
CSQ-8	Client satisfaction	(26)				x		
EQ-5D	Health-rel. quality of life	(27)		x		x	x	x
TIC-P	Resource use	(28)		x		x	x	x

12MFU = 12-month follow-up, 6MFU = 6-month follow-up, POST = post-treatment, PRE = pre-treatment (i.e., end of main phase), SN = screening, WK = weekly assessment (main phase week 1-9)

a) Suicidality item administered each week; patients contacted if flagged and referred to routine care as needed.

Data management

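### The week-3 alliance and credibility/expectancy ratings are hypothesised to correlate with both earlier and later improvement, but the planned correlations define no separate slope for either period

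*SAP*

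**What the plan says.** In the SAP, under Other indicators of common factors, both ratings come from one occasion: "At week 3, participants reported how they perceived the strength of the relationship with the therapist", with credibility and expectancy rated at the same time. Table 1 of the protocol agrees, listing the C/E scale and the WAI-6 at week 3 only. The same SAP section expects Pearson correlations of about 0.10-0.50 (credibility/expectancy) and 0.10-0.40 (alliance) "with previous and subsequent improvement in somatic symptom burden and symptom preoccupation". The hypotheses are thus defined relative to week 3.

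The analysis is in the SAP section Evaluation of exposure exercises, working alliance, and credibility/expectancy: "Pearson correlations will then be calculated to evaluate the relationship between working alliance and credibility/expectancy and change in somatic symptom burden (fitted slopes"), with the same wording for symptom preoccupation. Change is described as being over time, and no segment, break or window is given.

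Three other places bear on what a fitted slope means:
- The Statistical analysis plan section of the SAP says "models with a random intercept and slope will be built to capture unconditional growth in each of the putative mediators and outcomes", that is, one slope per process.
- The precedence models are restricted: "For outcomes and mediators both measured on a weekly basis, secondary analyses will explore week-by-week temporal precedence". Ratings taken once fall outside them.
- The protocol's Statistical analysis section names one spline, at post-treatment, and a possible quadratic time term. Neither is a break at week 3.

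**The concern.** The two hypotheses mean different things. A rating raised by early improvement supports only the first. The second, that the rating goes with improvement still to come, is the one that bears on mechanism. A single slope from pre- to post-treatment contains both periods, so one correlation would have to serve both hypotheses, and a result produced by early improvement could be reported as support for the later link.

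Timing adds to this. The SAP describes the ratings in the past tense and gives N=161, so enrolment appears to be complete. Unless the window is fixed in the SAP, it can be chosen after the results are seen.

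**Working it through.** **The plan's own figure.** The documents give no number for this analysis. The only design figure that can be recomputed is N=160 (d=0.5, 80% power, alpha 0.05, up to 20% loss): a t-test needs 64 per arm, 64/0.8 = 80, and 2 x 80 = 160. It reproduces. The point does not depend on it, except that n=80 is used below as one arm.

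**Step 1: weights, from the assessment grid alone.** The protocol schedule has pre, "WK = weekly assessment (main phase week 1-9") and post. Code these t = 0 to 10, with mean 5 and sum of (t-5)^2 = 110. Let each patient have slope b1 up to week 3 and b2 after it.
- Weight on b1: sum of (t-5) x min(t,3) = -4 - 6 - 6 + 3 x 14 = 26; 26/110 = 0.236.
- Weight on b2: sum of (t-5) x max(t-3,0) = -1 + 0 + 3 + 8 + 15 + 24 + 35 = 84; 84/110 = 0.764.

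The whole-period slope is therefore 0.236 b1 + 0.764 b2. This holds for least squares on complete, equally spaced data.

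**Step 2: what one correlation would show.** The documents give no SDs. Assume residual SD 2 (variance 4), independent early and late slopes, and the slope SDs s1/s2 below, in points per week. The variance of the fitted slope is V = (0.236 s1)^2 + (0.764 s2)^2 + 4/110. A rating with true correlation rho to early change only gives r = rho x 0.236 s1/sqrt(V). For later change only, r = rho x 0.764 s2/sqrt(V).

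| s1/s2 | early link only, rho 0.4 / 0.6 | later link only, rho 0.4 |
|---|---|---|
| 0.3/0.3 | 0.09 / 0.14 | 0.30 |
| 0.5/0.5 | 0.11 / 0.16 | 0.34 |
| 0.8/0.4 | 0.19 / 0.28 | 0.30 |

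All but the 0.09 lie inside both hypothesised ranges. Without measurement noise and with rho 0.4, early-slope SDs of 1, 2 and 3 times the later SD give 0.12, 0.21 and 0.27 for an early link only, and 0.38, 0.34 and 0.29 for a later link only. At the ratio of 3, opposite truths are almost indistinguishable.

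**Step 3: what two slopes cost.** Fit weeks 0-3 and 4-10 separately. The sums of squared time deviations are 5 and 28, so reliability is s1^2/(s1^2 + 4/5) = 0.10-0.44 early and s2^2/(s2^2 + 4/28) = 0.39-0.64 late. A true r of 0.4 is observed as 0.4 x sqrt(reliability): 0.13-0.27 early and 0.25-0.32 late. Power (Fisher z, two-sided 5%) is approximately Phi(atanh(r) x sqrt(n-3) - 1.96).

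| | n=80 | n=64 (20% loss) |
|---|---|---|
| Early slope, true r 0.4 | 20-67% | 17-57% |
| Later slope, true r 0.4 | 61-83% | 51-73% |

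For comparison, the whole-period slope has 77-88% power at n=80 when only the later link exists.

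A piecewise fit with a knot at week 3 does somewhat better. Its error variances are 4 x 0.1364 and 4 x 0.0213, against 4/5 and 4/28, so a true 0.4 is observed as 0.15-0.29 early and 0.29-0.34 late.

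**Step 4: what the split cannot do.** If each patient's slope is stable throughout and the rating is caused only by early change (rho 0.4 or 0.6), the whole-period r is 0.34-0.56 and the weeks 4-10 r is still 0.25-0.48.

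**The case against.** The strongest reply is that this is an omission and not a wrong analysis. The SAP nowhere says that a single whole-period slope will be correlated with the ratings, and its hypotheses already state the split. The one-slope model is set out for the Table 1 mediation tests, the correlation section does not refer to it, and the protocol allows a quadratic time term. This stands: a reader might infer that the SAP prescribes one slope, but that is an inference. What remains is that no text defines two slopes. If two are meant, the same clarification is needed.

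Second, the distortion may be small. With equal early and late slope SDs, a purely early link shows up as only 0.09-0.16, with a 13-29% chance of significance at n=80. It reaches 0.19-0.28 only where early slopes vary more than later ones. This stands too.

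Third, separate slopes are noisier, and the early one is weak. That is true and must be stated, but a more powerful test of a blended quantity does not answer either hypothesis.

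A reader might also infer that adding the ratings to the primary models, "In order to assess the relevance of the process variables as contributing to treatment effects", is invalid because part of the modelled change precedes the rating. The documents do not support that. As a plain covariate the rating leaves the time-by-group coefficient essentially unchanged, and the SAP does not mention a rating-by-time term. No change is asked for there.

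**Conclusion.** The gap is real and modest. The SAP poses a two-part question and specifies no analysis that separates the parts. If the one slope it describes is used, about 24% of that slope reflects change up to week 3 and 76% change after it, and a correlation inside the expected range cannot be assigned to either hypothesis.

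Only the weights come from the documents' schedule, and they assume least squares with complete, equally spaced data; the multilevel models with AR(1) errors planned for the trial would weight the weeks somewhat differently. All correlations, reliabilities and power figures rest on assumed SDs. The n=80 is also an assumption, because the SAP does not say whether these correlations are computed within arm.

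It would be too strong to conclude that splitting at week 3 establishes that the ratings drive later improvement; Step 4 shows otherwise. These are secondary correlations. The primary efficacy test and the Table 1 mediation tests are unaffected.

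**What to change.** In the SAP section on exposure exercises, working alliance and credibility/expectancy, define two slopes per outcome: previous (pre-treatment to week 3) and subsequent (week 3 to post-treatment). A piecewise growth model with a knot at week 3 is one way. It keeps the change from week 3 to week 4, the first after the rating, which separate fits to weeks 0-3 and 4-10 would drop. The knot also suits the recall period, since the outcome is a "1-week focus version of the Patient Health Questionnaire 15 (PHQ-15) as a measure of somatic symptom burden on a weekly basis" and the week-3 score therefore describes the week leading up to the rating. Report each rating's Pearson correlation with each slope, with confidence intervals, and say whether the correlations are within arm or pooled.

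State three limitations:
- The early slope rests on four assessments, so a true 0.4 may appear as about 0.13-0.27, with power of about 20-67% at n=80. A null result there is weak evidence.
- Power for the later slope is about 61-83%, somewhat below that of a whole-period slope.
- A correlation with the later slope does not rule out reverse causation if individual slopes are stable.

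The cost is a few sentences in the SAP. The weekly PHQ-15 and SSD-12 scores are already collected, so no new data are needed.

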The annual societal cost of medically unexplained symptoms in Sweden is approximately 40 billion SEK (1), i.e., similar to the annual cost of cancer (2). Prevalent chronic diseases like asthma and diabetes are also commonly associated with somatic symptoms that lead to significant distress and pervasive behavioral changes that result in functional impairment and place added strain on the health care system. Exposure-based treatment, where the patient willingly engages with stimuli that give rise to unwanted physical sensations or distress, has shown promise in reducing somatic symptom load and increasing quality of life in several conditions where patients commonly report substantial distress related to somatic symptoms, such as in asthma (3), musculoskeletal pain (4), and functional gastrointestinal syndromes (5). In routine care, however, access to such exposure-based treatment is limited. One reason for this is probably that there exists no flexible exposure-based treatment protocol that can be easily tailored to suit a wide spectrum of patient groups who suffer from distress related to recurrent somatic symptoms. In a recent single group feasibility trial (N=33) at Karolinska Institutet, Sweden, we found that such a tailored exposure-based treatment delivered in an online text-based format can be acceptable, with high treatment adherence, adequate treatment satisfaction, large and lasting within-group improvement, and no serious adverse events. This is a randomized controlled trial (N=160) where we aim to test if the same tailored internet-delivered exposure-based treatment is more efficacious than a standardized education control for adult patients with clinically significant distress related to somatic symptoms in a primary care setting. Primary outcome is change in self-rated somatic symptom burden as modelled using linear mixed models fitted on weekly Patient Health Questionnaire 15 sum scores over the treatment period. Long-term efficacy is assessed up to one year after treatment and cost-effectiveness is investigated based on the incremental cost-effectiveness ratio. We expect this trial to be of notable clinical importance as it will be indicative of the usefulness of a broad exposure-based treatment protocol for distress related to somatic symptoms in primary care.

Overview of the field (background)

Recurrent distress associated with somatic symptoms: a common and costly problem

Approximately one fifth of primary care patients seek care for symptoms that cannot readily be given a medical explanation (6, 7). In addition, primary care is tasked with offering care for prevalent chronic diseases such as asthma and diabetes where somatic symptoms often lead to distress and pervasive behavioral changes. Though a concern with somatic symptoms can be fully warranted, helpful, and transient, it can also be persistent and lead to much unnecessary suffering. Existing treatments commonly yield insufficient effects on medically unexplained symptoms (8). Based on inflation-adjusted British estimates (1), the annual Swedish societal cost of medically unexplained symptoms is probably about 40 billion SEK, i.e., similar to the annual cost of cancer (2).

Symptom preoccupation as a therapeutic target

Psychological factors – in particular the preoccupation with symptoms – have been found to affect the perception and intensity of a large number of physical symptoms, both with and

without a clear medical genesis (9). In pain, it has for example been found that fear and the preoccupation with symptoms can have a more substantial predictive value for chronicity than pain itself (10). In general, in individuals who suffer from clinically significant symptom preoccupation, behaviors intended to evaluate symptoms, seek information about symptoms, or avoid discomfort have been found to often contribute to worsened function and increased symptom burden in the long term (11).

Diagnosis-specific exposure-based treatment often efficacious

This makes exposure, where the patient willingly and systematically approaches stimuli that give rise to unwanted symptoms or discomfort while refraining from acting on symptoms, a logical intervention. There are several examples where exposure-based treatment has been found to be efficacious when protocols were written to suit a particular group of patients where distress associated with somatic symptoms is common, e.g., a particular functional somatic syndrome in terms of fibromyalgia and irritable bowel syndrome (4, 5), or a chronic somatic condition such as asthma or atrial fibrillation (3, 12). Typically, effects on symptoms and the preoccupation with symptoms have been large (3-5, 12), and there is evidence to suggest that a reduction in somatic symptom burden may have been mediated by a reduction in symptom preoccupation or behaviors that serve to reduce distress in the short term (13).

Need for a more flexible exposure-based approach

Generalist primary care clinics typically do not have the resources necessary for administering specific psychological treatments for a large number specific functional somatic syndromes or chronic somatic conditions (14). We suspect that a more general treatment protocol that can be tailored to suit a wide spectrum of physical symptoms could dramatically improve access to exposure-based treatment for patients with distress related to somatic symptoms. This may be particularly true if treatment can be delivered via the internet, which requires less therapist time but often results in similar effects as face-to-face treatment (15).

Promising feasibility trial

We recently completed a feasibility trial at Karolinska Institutet, Sweden (NCT04511286), where we found that an internet-delivered flexible exposure-based treatment for individuals with high levels of symptom preoccupation regardless of somatic symptom domain (N=33; e.g., functional gastrointestinal symptoms, atrial fibrillation, migraine) can be delivered with high treatment adherence, adequate client satisfaction, large and lasting improvement in self-reported somatic symptoms and symptom preoccupation, and no serious adverse events. It is thus motivated to evaluate this treatment format further.

Need for a randomized controlled trial in a routine clinical setting

In further evaluating the flexible exposure-based treatment approach for patients with distress related to somatic symptoms it is imperative to conduct a randomized controlled trial versus an informative control condition, focusing on effects on somatic symptoms and symptom preoccupation. It is also important to evaluate if the treatment can be effective in a routine clinical setting and when patients are referred via a clinician such as a general practitioner.

Aim of the clinical trial

This trial aims to evaluate if flexible internet-delivered exposure-based treatment is more effective than an internet-delivered standardized routine care education program for patients with distress related to somatic symptoms in primary care.

Primary research question

- Compared to the control condition, does flexible internet-delivered exposure-based treatment lead to a larger improvement in self-rated somatic symptom burden as assessed using the Patient Health Questionnaire 15 (PHQ-15)? Hypothesis: Yes.

Key secondary research questions

- Compared to the control condition, does flexible internet-delivered exposure-based treatment lead to a larger improvement in symptom preoccupation, psychiatric symptom burden, and functional impairment? Hypothesis: Yes.
- In flexible internet-delivered exposure-based treatment, are effects maintained up to 12 months after treatment? Hypothesis: Yes.
- Is flexible internet-delivered exposure-based treatment cost-effective compared to the control condition? Hypothesis: Yes.
- Is the controlled effect of the flexible exposure-based treatment on self-rated somatic symptoms moderated by baseline symptoms and preoccupation? Hypothesis: Yes.
- Is the effect of the flexible exposure-based treatment on self-rated somatic symptom burden mediated by a reduction in symptom preoccupation? Hypothesis: Yes.

Methods

Design and power

Randomized controlled trial of flexible internet-delivered exposure-based treatment for distress related to somatic symptoms, based at Liljeholmen academic primary care clinic, Stockholm, Sweden. Patients (N=160) who report being bothered by somatic symptoms (and who may or may not meet criteria for a diagnosis where distress related to symptoms is common, such as fibromyalgia or asthma), who express interest in psychological treatment, and who's medical status does not make exposure therapy unsuitable are randomized (1:1), in consecutive even numbered cohorts, to flexible internet-delivered exposure-based treatment or an internet-delivered standardized education control. The trial is powered to enable the study of moderate between-group effects ($d=0.5$) as based on mean tests with 80% power, given $\alpha=0.05$ and up to 20% data loss.

Eligibility criteria

- a) (i) Either much bothered by at least one somatic symptom (2 points on at least one item of the PHQ-15) or at least a moderate overall somatic symptom burden (PHQ-15 sum 10 points (16)), with (ii) recurrent distress related to somatic symptoms ≥ 4 months
- b) Symptoms not best explained by, and clinical picture not dominated by, severe health anxiety (where an established treatment already exists (17)) or a non-somatoform psychiatric disorder such as depression, panic disorder, primary insomnia, or a chronic stress disorder
- c) Affirms that he or she is interested in completing an intense psychological treatment with the aim of reducing distress associated with physical symptoms
- d) Adult (≥ 18 years old)
- e) Living in Stockholm County
- f) Can read and write in Swedish
- g) Not severe psychiatric condition or suicidal ideation

Exposure-based treatment vs. standardized education for distress related to somatic symptoms
Study protocol intended for peer review

- h) No clear medical risk in taking part in exposure-based treatment (e.g., pregnancy) and somatic condition, or treatment for somatic condition, does not make treatment unfeasible
- i) Continuous psychotropic medication (antidepressants, anticonvulsants, mood-stabilizers, antipsychotics) either non-existent or stable since at least 4 weeks, and expected to remain stable over the main phase of the trial
- j) Not severe alcohol or substance use disorder likely to interfere with treatment
- k) Not planned absence for more than 1 week during the intended main phase
- l) Complete pre-treatment assessment

Instruments

Psychiatric assessment is based on the Mini-International Neuropsychiatric Interview (MINI (18)) and Health Preoccupation Diagnostic Interview (HPDI (19)). Primary outcome measure is somatic symptom burden as assessed using the Patient Health Questionnaire 15 (PHQ-15 (16)). Secondary outcomes are: symptom preoccupation (SSD-12 (20); SYMPS-prel), general anxiety (GAD-7 (21)), depression (PHQ-9 (22)), disability (WHODAS 2 (23)), credibility and expectancy (C/E scale (24)), relation with the therapist (WAI-6, (25)), client satisfaction (CSQ-8 (26)), negative effects (free-text questions), quality of life (EQ-5D (27)), and societal resource use (TIC-P (28)). Health anxiety (HAI-14, (29)) and alcohol/drug use (AUDIT, DUDIT (30, 31)) are assessed for the purpose of screening only. Eleven questions concerning the basis of subjective somatic symptom burden in terms of symptom severity, disability, and emotional components will also be administered at baseline so as to facilitate the interpretation of the PHQ-15.

[figure not shown]

Figure 1. Schematic overview of participant flow

Procedure

We aim to recruit Swedish adults with recurrent distress related to somatic symptoms and an interest in psychological treatment. Patients will be referred via regular services including

Exposure-based treatment vs. standardized education for distress related to somatic symptoms
Study protocol intended for peer review

general practitioners, the psychosocial team, and waiting room advertisement at Liljeholmen primary care clinic in southern Stockholm (Figure 1). If the rate of inclusion is too slow, patients will also be referred from other clinics of Stockholm, and, if necessary, based on newspaper and social media advertisement. Those interested in the trial are referred to the study website where they are given extensive information about the trial and contact information for the principal investigator. The data management plan is described in sufficient detail, and it is made clear that participants of the trial retain their right to take part in routine care services, and also to cancel their participation at any point without further justification. Visitors of the website are then given the option of providing informed consent via an encrypted online form, prior to which no information is collected. This is a common and secure method of providing informed consent, see for example EPM id 2020-01740.

Once informed consent has been provided, the applicant is granted a personal account on the secure online measurement platform and is prompted to provide data on identity and sociodemographic variables including age, gender, and educational attainment. Then follows a series of self-report questionnaires and questions about key clinical variables including medications, diagnoses, and prior treatment. The purpose of this screening assessment (“SN” in Table 1) is to collect sufficient data to ensure reliable assessment of eligibility criteria (above) and enable adequate description of the sample.

After having completed the screening, applicants are contacted for a psychiatric assessment (primarily the MINI) and eligibility interview with a mental health clinician. As is routine practice at the clinic, this may be conducted face-to-face, via telephone, or via a secure video conferencing service. As is routinely done in the primary care clinic, the patient’s general practitioner is consulted whenever further medical evaluation is deemed necessary. Applicants who do not meet eligibility criteria a-k are excluded and referred to routine care, at the clinic if possible, and in accordance with regional healthcare guidelines. Applicants who meet eligibility criteria a-k are encouraged to complete the pre-treatment assessment. Those who do so are randomized (1:1) to flexible internet-delivered exposure-based treatment or the education control and are thereby included as participants in the trial. The subsequent 10 weeks constitute the main phase of the trial during which key measures are administered on a weekly basis (Table 1). At the end of the main phase follows the post-treatment assessment. Follow-up assessments follow 6 and 12 months after therapy.

Table 1. Key outcome measures and assessment points

Questionnaire	Outcome	Reference	SN	PRE	WK	POST	6MFU	12MFU
PHQ-15 (prim.)	Somatic symptoms	(16)	x	x	x	x	x	x
SSD-12	Symptom preoccupation	(20)	x	x	x	x	x	x
SYMPS-prel	Symptom preoccupation	Prel. version	x	x	x	x	x	x
GAD-7	Anxiety	(21)		x		x	x	x
PHQ-9 ^a	Depression	(22)	x	x		x	x	x
WHODAS 2.0	Disability	(23)	x	x		x	x	x
HAI-14	Health anxiety	(29)	x					
AUDIT, DUDIT	Alcohol, drug use	(30, 31)	x					
C/E scale	Credibility/expectancy	(24)			w. 3			
WAI-6	Relationship w. therapist	(25)			w. 3			
CSQ-8	Client satisfaction	(26)				x		
EQ-5D	Health-rel. quality of life	(27)		x		x	x	x
TIC-P	Resource use	(28)		x		x	x	x

12MFU = 12-month follow-up, 6MFU = 6-month follow-up, POST = post-treatment, PRE = pre-treatment (i.e., end of main phase), SN = screening, WK = weekly assessment (main phase week 1-9)

a) Suicidality item administered each week; patients contacted if flagged and referred to routine care as needed.

Data management

